9.2.2. Serious Adverse Events

An SAE is any AE from this study that results in one of the following outcomes:

- death
- initial or prolonged inpatient hospitalization
- a life-threatening experience (that is, immediate risk of dying)
- persistent or significant disability/incapacity
- congenital anomaly/birth defect
- considered significant by the investigator for any other reason: important medical events that may not result in death, be life-threatening, or require hospitalization may be considered serious, based upon appropriate medical judgment

Although all AEs after signing the ICF are recorded in the CRF, SAE reporting begins after the patient has signed the ICF and has received investigational product. However, if an SAE occurs after signing the ICF, but prior to receiving investigational product or PET imaging, it needs to be reported ONLY if it is considered reasonably possibly related to study procedure.

Study site personnel must alert Lilly or its designee of any SAE within 24 hours of investigator awareness of the event via a sponsor-approved method. If alerts are issued via telephone, they are to be immediately followed with official notification on study-specific SAE forms. This 24-hour notification requirement refers to the initial SAE information and all follow-up SAE information.

Pregnancy (during maternal or paternal exposure to investigational product) does not meet the definition of an AE. However, to fulfill regulatory requirements any pregnancy should be reported following the SAE process to collect data on the outcome for both mother and fetus.

Investigators are not obligated to actively seek AEs or SAEs in patients once they have discontinued and/or completed the study (the patient summary CRF has been completed). However, if the investigator learns of any SAE, including a death, at any time after a patient has been discharged from the study, and he/she considers the event reasonably possibly related to the study treatment or study participation, the investigator must promptly notify Lilly.

9.2.2.1. Suspected Unexpected Serious Adverse Reactions

Suspected unexpected serious adverse reactions (SUSARs) are serious events that are not listed in the IB and that the investigator identifies as related to investigational product or procedure. United States 21 CFR 312.32 and European Union Clinical Trial Directive 2001/20/EC and the associated detailed guidances or national regulatory requirements in participating countries require the reporting of SUSARs. Lilly has procedures that will be followed for the recording and expedited reporting of SUSARs that are consistent with global regulations and the associated detailed guidances.

9.2.2.2. Adverse Events of Special Interest

Adverse events associated with specific TEAE clusters will be monitored. The TEAE clusters of interest include:

- Infusion-related reactions
- TEAEs associated with anti-solanezumab antibodies (immunogenicity)
- ARIA-H (amyloid-related imaging abnormality—hemorrhage/hemosiderin deposition, also known as cerebral microhemorrhage)
- ARIA-E
- Hemorrhagic stroke and microhemorrhage
- Cardiac ischemia-related events
- Cardiac arrhythmia-related events

Data on cerebro-cardiovascular events (for example, death, myocardial infarction, stroke, etc.) will be adjudicated by an external Clinical Endpoint Committee (CEC). The role of the CEC is to adjudicate defined clinical events, in a blinded, consistent, and unbiased manner throughout the course of a study. Complete details will be available in the CEC charter.

9.2.3. Complaint Handling

Lilly collects product complaints on investigational products and drug delivery systems used in clinical studies in order to ensure the safety of study participants, monitor quality, and to facilitate process and product improvements.

Patients will be instructed to contact the investigator as soon as possible if he or she has a complaint or problem with the investigational product so that the situation can be assessed.

9.3. Other Safety Assessments

9.3.1. Physical Examinations and Neurologic Examination

Physical and neurological examinations will be conducted as specified in the Schedule of Activities (Section 2) and as clinically indicated.

Physical examinations will include assessment of general appearance, skin, head and neck, lymph nodes, thyroid, abdomen (bowel sounds and liver and spleen palpation), back (costovertebral angle tenderness), and musculoskeletal, cardiovascular, and respiratory systems. Neurological examinations will include assessment of cranial nerves, motor and sensory systems, muscle stretch reflexes, balance and coordination, and gait. The physical and neurological

examination will be performed by a physician, nurse practitioner, or physician's assistant (for Japan, physician only).

Body weight and height will be recorded according to the Schedule of Activities (Section 2).

If a clinically meaningful change in an MRI is noted during the study, an additional full neurological exam will be performed as soon as possible, along with any other medical follow-up deemed necessary by the investigator.

Any clinically significant change from baseline on follow-up physical and neurological examinations should be reported to Lilly or its designee as an AE via CRF.

9.3.2. *Electrocardiograms*

For each patient, ECGs should be collected according to the Schedule of Activities (Section 2). Electrocardiograms should be recorded according to the study-specific recommendations included in the manual of operations for the study.

Electrocardiograms will initially be interpreted by a qualified physician (the investigator or qualified designee) at the site as soon after the time of ECG collection as possible, and ideally while the patient is still present, to determine whether the subject meets entry criteria and for immediate patient management, should any clinically relevant findings be identified.

All ECGs will be electronically transmitted to a designated central ECG laboratory. A cardiologist at the central ECG laboratory will then conduct a full overread. A report based on data from this overread will be issued to the investigative site. When there are differences in ECG interpretation between the local and central readings, the locally read interpretation will be used for study entry and immediate patient management, and the centrally read interpretation will be used for data analysis and report writing purposes.

Any clinically significant findings from ECGs that result in a diagnosis and that occur after the patient receives the first dose of the investigational treatment should be reported to Lilly or its designee as an AE via CRF.

9.3.3. *Vital Signs*

For each patient, vital signs measurements should be conducted according to the Schedule of Activities (Section 2) and following the study-specific recommendations included in the manual of operations for the study.

Any clinically significant findings from vital signs measurement that result in a diagnosis and that occur after the patient receives the first dose of study treatment should be reported to Lilly or its designee as an AE via CRF.

9.3.4. *Body Weight and Height*

Body weight and height will be recorded according to the Schedule of Activities (Section 2).

9.3.5. Laboratory Tests

For each patient, laboratory tests detailed in (Appendix 2) should be conducted according to the Schedule of Activities (Section 2).

Any clinically significant findings from laboratory tests that result in a diagnosis and that occur after the patient receives the first dose of investigational product should be reported to Lilly or its designee as an AE via CRF.

9.3.6. Magnetic Resonance Imaging

Magnetic resonance imaging of the brain will be performed according to the Schedule of Activities (Section 2) and as clinically indicated. This technology will be used to check for evidence of hemorrhage/hemosiderin deposition (ARIA-H, also known as cerebral microhemorrhage) and edema/effusions (ARIA-E, also known as cerebral vasogenic edema). (The volumetric MRI data will also be used to calculate brain volumes.) The MRI scans will be sent for analysis to a centralized MRI vendor designated by Lilly. The scans will be reviewed by the investigator or qualified designee for immediate patient management or assessment of patient's study eligibility as appropriate. Any clinically significant findings noted at baseline that result in a diagnosis should be recorded as a preexisting condition or AE. Specific analyses of the scans, including assessments of ARIA-H and ARIA-E and calculations of brain volumes, will subsequently be interpreted by the centralized MRI vendor for data analysis and report-writing purposes. Results of centrally read MRIs regarding patient care/safety will be reported back to sites even though there was a local read.

9.3.7. Columbia Suicide Severity Rating Scale (Adult Version)

Consistent with Food and Drug Administration (FDA) regulatory guidance (FDA 2012), any occurrence of suicide-related thoughts and behaviors will be assessed as indicated in the Schedule of Activities (Section 2) using the Columbia Suicide Severity Rating Scale (C-SSRS), a scale that captures the occurrence, severity, and frequency of suicide-related thoughts and behaviors during the corresponding assessment period. The scale includes suggested questions to elicit the type of information needed to determine if a suicide-related thought or behavior occurred.

Terms captured by the use of the C-SSRS can be mapped to Columbia Classification Algorithm for Suicide Assessment (Posner et al. 2007) to facilitate future pooling of data.

The first time the scale is administered in this study, the C-SSRS "Baseline" version will be used, and the findings will constitute the baseline assessment. The C-SSRS "Since Last Visit" scale will be used for all subsequent assessments. If a suicide-related thought or behavior is identified at any time during the study, a thorough evaluation will be performed by a study physician, and appropriate medical care will be provided. The Lilly Self-Harm Supplement should be completed every time the C-SSRS is administered. If, based on administration of the C-SSRS, it is determined that suicide-related behaviors have occurred, then the Lilly Self-Harm Follow-Up form will be used to collect additional information to allow for a more complete assessment of these behaviors.

9.3.8. Safety Monitoring

Lilly will periodically review evolving aggregate safety data within the study by appropriate methods. In addition, unblinded data on safety-related measures and SAEs will be periodically reviewed by a Data Monitoring Committee (DMC; Section 10.8) until database lock of the double-blind period. Complete details will be available in the DMC charter.

If a study patient experiences elevated ALT $\geq 3X$ ULN, ALP $\geq 2X$ ULN, or elevated TBL $\geq 2X$ ULN, clinical and laboratory monitoring should be initiated by the investigator. Details for hepatic monitoring depend upon the severity and persistence of observed laboratory test abnormalities. To ensure patient safety and comply with regulatory guidance, the investigator is to consult with the Lilly CRP regarding collection of specific recommended clinical information and follow-up laboratory tests. See [Appendix 3](#).

In the event that blinded safety monitoring identifies an issue that may need to be addressed by unblinding at the group level, those blinded individuals may recommend to members of the DMC that they should conduct additional analyses of the safety data.

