- a If desired, the following visits may take place over 2 consecutive days: Visit 2 (randomization visit), Visit 15 (Week 52), Visit 28 (Week 104), and ED. If done over 2 days, it is recommended that the following procedures be performed on Day 2: CDR-SB, RBANS, NPI, and FCSRT, as applicable. Dosing should occur at the end of the second day.
- b Visits should be scheduled as close as possible to the intended week in relation to baseline. Furthermore, visits must be scheduled such that study drug administration never occurs at intervals of less than 21 days.
- c All patients will have either a florbetapir PET scan or lumbar puncture at screening to determine eligibility. If florbetapir PET scan is used, this procedure will be repeated at the 24-month endpoint (or early discontinuation). If LP is used, then a second LP will be administered at 1 later time point, with LP patients being assigned by the IWRS to have the second LP at Week 4, 8, 12, 24, 52, 76, or 104 (or ED). Opting out of the 2nd LP will not be considered a protocol deviation. Any CSF collected via LP as part of the main study or the optional LP addendum will be analyzed for A β s, tau proteins, solanezumab, and biomarker storage. LPs are to be performed before study drug administration. It will not be considered a protocol deviation if the LP is not performed or if CSF is not collected for storage and future analysis in countries prohibiting sample storage. Patients undergoing LP will have PT/INR, PTT, and platelet count tested prior to each LP.
- d Pharmacokinetic samples should be obtained immediately before dosing at all designated visits. In addition, postdose samples should be taken at Visits 2 and 5.
- e Visit 301 should be scheduled to occur 4 months after last dose (that is, 3 months after Visit 28 or in case of ED, 4 months after last dose).

3. Introduction

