- Adverse event: If the investigator decides that the patient should be withdrawn from the study because of an SAE or a clinically significant laboratory value, the investigational product is to be discontinued and appropriate measures are to be taken. Lilly or its designee is to be alerted immediately (Section 8.2).

In addition, patients *may* be discontinued from the study drug and from the study in the following circumstances, and if discontinued, will undergo early discontinuation procedures as shown in the Schedule of Activities (Section 2):

- Appearance of clinically significant new cerebral ischemic or hemorrhagic events or ARIA-E (amyloid-related imaging abnormality—edema/effusions, also known as cerebral vasogenic edema) by MRI (Section 9.3.6); patients with new MRI findings can continue to participate in the study depending on clinical significance as determined by the investigator.

Note: While most cases of ARIA-E are asymptomatic, when symptoms do occur they are reported to be most commonly headache, worsening of cognitive function, alteration of consciousness, seizures, unsteadiness, and vomiting. Even when symptomatic ARIA-E is present, in most cases treatment is not required beyond discontinuation of the study medication until the imaging abnormalities are resolved. If a patient simultaneously develops more than one of the symptoms suggestive of ARIA-E; that is, headache, worsening of cognitive function, alteration of consciousness, seizures, unsteadiness, or vomiting, then an unscheduled MRI may be obtained. A single symptom suggestive of ARIA-E of sufficient severity may also warrant an MRI. The unscheduled MRI should be performed in the same manner as the currently scheduled MRIs in the protocol, which includes sending the images for central review.

- Discontinuation of the investigational product for abnormal liver tests **should be considered** by the investigator when a patient meets one of the following conditions after consultation with the Lilly designated medical monitor:
 - ALT or AST >8X ULN
 - ALT or AST >5X ULN for more than 2 weeks
 - ALT or AST >3X ULN and total bilirubin level (TBL) >2X ULN or prothrombin time >1.5X ULN
 - ALT or AST >3X ULN with the appearance of fatigue, nausea, vomiting, right upper-quadrant pain or tenderness, fever, rash, and/or eosinophilia (>5%)
 - alkaline phosphatase (ALP) >3X ULN
 - ALP >2.5X ULN and TBL >2X ULN

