Appendix 2. Clinical Laboratory Tests

Clinical Laboratory Tests

Hematology^a

Hemoglobin
 Hematocrit
 Erythrocyte count (RBC)
 Mean cell volume
 Mean cell hemoglobin concentration
 Leukocytes (WBC)
 Neutrophils, segmented
 Lymphocytes
 Monocytes
 Eosinophils
 Basophils
 Platelets

Clinical Chemistry^a

Serum Concentrations of:

Sodium
 Potassium
 Total bilirubin
 Direct bilirubin
 Alkaline phosphatase
 Alanine aminotransferase (ALT)
 Aspartate aminotransferase (AST)
 Blood urea nitrogen (BUN)
 Creatinine
 Uric acid
 Calcium
 Glucose, nonfasting
 Albumin
 Cholesterol
 Creatine kinase (CK)

Pregnancy Test (females only)^{b,c}

Lumbar Puncture (screening or optional)^{a, d}

Solanezumab
 A β proteins
 Tau proteins

Abbreviations: A β = amyloid- β peptide; LP = lumbar puncture; PET = positron emissions tomography; RBC = red blood cells; WBC = white blood cells.

^a Assayed by Lilly-designated (central) laboratory.

^b Assayed by local or investigator-designated laboratory.

^c Female patients of childbearing potential must test negative on a serum pregnancy test at screening and must test negative on a urine pregnancy test on the day of any PET scan, prior to the administration of radiopharmaceutical agent.

^d Patients who undergo LP will have coagulation panel (prothrombin time [PT]/International Normalized Ratio [INR] and partial thromboplastin time [PTT]) and platelet count) obtained from a local laboratory up to 4 weeks before each LP.

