Appendix 3. Hepatic Monitoring Tests for Treatment-Emergent Abnormality

Selected tests may be obtained in the event of a treatment-emergent hepatic abnormality and may be required in follow-up with patients in consultation with the Lilly, or its designee, clinical research physician.

Hepatic Monitoring Tests

Hepatic Hematology^a

Hemoglobin
Hematocrit
RBC
WBC
Neutrophils, segmented
Lymphocytes
Monocytes
Eosinophils
Basophils
Platelets

Hepatic Chemistry^a

Total bilirubin
Direct bilirubin
Alkaline phosphatase
ALT
AST
GGT
CPK

Haptoglobin^a

Hepatic Coagulation^a

Prothrombin Time
Prothrombin Time, INR

Hepatic Serologies^{a,b}

Hepatitis A antibody, total
Hepatitis A antibody, IgM
Hepatitis B surface antigen
Hepatitis B surface antibody
Hepatitis B Core antibody
Hepatitis C antibody
Hepatitis E antibody, IgG
Hepatitis E antibody, IgM

Anti-nuclear antibody^a

Alkaline Phosphatase Isoenzymes^a

Anti-smooth muscle antibody (or anti-actin antibody)^a

Abbreviations: ALT = alanine aminotransferase; AST = aspartate aminotransferase; CPK = creatinine phosphokinase; GGT = gamma-glutamyl transferase; Ig = immunoglobulin; INR = international normalized ratio; RBC = red blood cells; WBC = white blood cells.

^a Assayed by Lilly-designated or local laboratory.

^b Reflex/confirmation dependent on regulatory requirements and/or testing availability.

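### Section 9.3.8 starts hepatic monitoring on ALT, ALP or bilirubin but not AST, although every transaminase criterion in section 8.2 applies to ALT or AST

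*Protocol*

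**What the plan says.** Protocol section 9.3.8 (Safety Monitoring) sets three hepatic triggers: ALT ≥3X ULN, ALP ≥2X ULN and total bilirubin (TBL) ≥2X ULN. When one is reached, "clinical and laboratory monitoring should be initiated by the investigator", and "the investigator is to consult with the Lilly CRP regarding collection of specific recommended clinical information and follow-up laboratory tests". AST does not appear in the list.

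Protocol section 8.2 (Discontinuation from the Study) lists the liver-test conditions under which stopping the investigational product should be considered "by the investigator when a patient meets one of the following conditions after consultation with the Lilly designated medical monitor". Four of them concern transaminases, and each covers ALT or AST. Two matter most here: "ALT or AST >5X ULN for more than 2 weeks" and "ALT or AST >3X ULN and total bilirubin level (TBL) >2X ULN or prothrombin time >1.5X ULN".

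On the tests those criteria need:

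- **Chemistry.** The Schedule of Activities places chemistry at Visit 1 (Week -4), Weeks 24, 52, 76 and 104, and early discontinuation. Appendix 2 includes AST in that panel.
- **Prothrombin time (PT).** Schedule footnote c ties PT to lumbar puncture (LP): "Patients undergoing LP will have PT/INR, PTT, and platelet count tested prior to each LP". Appendix 2 footnote d agrees and allows the sample up to 4 weeks before the LP.
- **Follow-up panel.** Appendix 3 lists both AST and PT. It makes the tests available for a treatment-emergent hepatic abnormality and adds that they "may be required in follow-up with patients in consultation with the Lilly, or its designee, clinical research physician".

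**The concern.** An early-warning rule should fire no later than the decision rule it feeds. For ALT, ALP and bilirubin it does. For AST there is no early rule, although section 8.2 gives AST the same standing as ALT.

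Take an asymptomatic patient with AST at 6X ULN at Week 24, no eosinophilia, and ALT, ALP and TBL all below their 9.3.8 triggers. Two 8.2 conditions are open: persistence above 5X for more than 2 weeks, and a raised PT. Neither can be judged without another test, and 9.3.8 does not prompt one. Whether the test is ordered then depends on what the investigator infers from 8.2, on permissive text and on general duties of care. At stake is consistent follow-up between investigators.

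**Working it through.** The plan states no figure on this point to reproduce. The check compares the two sections and counts branches and schedule gaps.

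**1. Early trigger against discontinuation criteria**

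| Analyte | 9.3.8 trigger | Lowest level used in 8.2 | Trigger at or below that level? |
|---|---|---|---|
| ALT | ≥3X | >3X (with TBL, PT or symptoms/eosinophilia) | Yes |
| ALP | ≥2X | >2.5X (with TBL or symptoms/eosinophilia) | Yes |
| TBL | ≥2X | >2X (only in combination) | Yes |
| AST | none | >3X (same as ALT) | No trigger |

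AST is named in 4 of 4 transaminase criteria in 8.2 and in 0 of 3 triggers in 9.3.8.

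**2. AST branches in 8.2**

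The third criterion is read as >3X AND (TBL >2X OR PT >1.5X). Splitting it gives five branches.

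| AST branch | Further test needed after an isolated rise? |
|---|---|
| >8X | No; one sample decides |
| >5X for more than 2 weeks | Yes; repeat AST |
| >3X with TBL >2X | No; bilirubin itself fires 9.3.8 |
| >3X with PT >1.5X | Yes; PT |
| >3X with symptoms or eosinophilia | No |

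Two of five need a further test.

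**3. When the schedule next supplies an AST**

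- Planned gaps after a first high value at Week 24, 52 or 76: 52 − 24 = 28 weeks; 76 − 52 = 24 weeks; 104 − 76 = 28 weeks.
- Ratio to the 2-week duration: 28/2 = 14; 24/2 = 12; 28/2 = 14.
- The gaps span 7, 6 and 7 visit intervals. At the 21-day minimum these are 147, 126 and 147 days, or 21, 18 and 21 weeks (10.5, 9 and 10.5 times 2 weeks).
- Infusions strictly between draws: Weeks 28 to 48 = 6; Weeks 56 to 72 = 5; Weeks 80 to 100 = 6. These would all be given before the next AST only if nothing is ordered meanwhile, which is a worst-case assumption.
- A first rise at Week 104 or early discontinuation has no later scheduled chemistry (none at Visit 301), but dosing has then ended.

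**4. When the schedule supplies a PT**

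- Patients qualified by PET and outside the LP addendum: none.
- Patients qualified by LP, main study: at most two, before the screening LP and the second LP.
- Possible second-LP weeks are 4, 8, 12, 24, 52, 76 and 104; 4 of these 7 (24, 52, 76, 104) are chemistry visits. Even then the PT precedes the LP and is not a response to an AST result.

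**5. What is specific to AST**

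Steps 3 and 4 come from the visit schedule and hold equally for ALT. Only step 1 separates the two enzymes: a high ALT brings an instruction to monitor and consult, and a high AST does not.

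**The case against.** The case for leaving the text alone has four parts.

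*Other provisions already cover AST.* Section 8.2 has its own medical-monitor consultation, and a criterion with a 2-week duration implies a repeat AST. Appendix 3 is not limited to ALT and lists AST and PT. Section 9.2 requires documented review of each laboratory report and follow-up of important adverse events, and 9.3.8 adds periodic aggregate review by the sponsor and the monitoring committee. The consultation sentence in 9.3.8 could also be read more broadly than the trigger before it. All this stands as mitigation, and it means that follow-up is not barred. It does not replace the cue: the 8.2 consultation attaches to a condition that may not be demonstrable until the test is done, Appendix 3 is permissive, and the broader reading of 9.3.8 is inference.

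*The omission may be deliberate.* Exclusion criterion [22] uses ALT ≥2X but AST ≥3X, so the protocol does treat AST more leniently at entry. That does not explain dropping AST from the trigger when 8.2 applies identical thresholds to both enzymes.

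*The large ratios are not caused by the omission.* This is correct. A reader might infer that the 12- to 14-fold gaps and the 5 or 6 intervening infusions measure the effect of leaving AST out. They do not: they apply to ALT too, and adding AST to the trigger would not remove them.

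*The example could hardly arise in this trial.* SAP section 6.1 says the study was stopped about 6 months after the first subject entered. Week 52 is 13 visit intervals, or 13 × 21 days = 39 weeks at the shortest spacing, so no patient would be expected to have crossed the Week 24 to 52 gap on treatment. Early-discontinuation chemistry supplied the next draw. The point is therefore about the design.

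**Conclusion.** The point holds as a small misalignment between two sections. An isolated AST rise has no explicit trigger in 9.3.8, while 8.2 uses AST on the same terms as ALT. Two of five AST branches need a test that the schedule does not deliver in time. The defect specific to AST is the missing cue to start monitoring and consult, and nothing more.

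Two stronger readings are not supported:

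- That the schedule never provides the tests. It repeats AST 24 to 28 weeks later or at early discontinuation, and it provides PT before lumbar punctures.
- That a required stop could be missed. The 8.2 liver criteria are discretionary, to be considered after consultation.

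The count of five branches assumes the AND/OR reading of the third criterion given in the working. The documents give no frequency of isolated AST rises; few patients are likely to be affected. With 26 patients randomized before the sponsor stopped the study, the practical effect here is essentially nil. This is a cheap improvement of minor impact, worth considering wherever this text is used again.

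**What to change.** Change the 9.3.8 trigger to: **ALT or AST ≥3X ULN, ALP ≥2X ULN, or TBL ≥2X ULN**. Monitoring and consultation would then start for AST on the same terms as for ALT.

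The change adds two words and no scheduled test, since AST is already measured at every chemistry visit and both AST and PT are already in Appendix 3. The cost is a few unscheduled liver tests. Some would follow non-hepatic AST rises, and some would be in patients who entered just under the 3X ULN AST limit in criterion [22] and cross it on a small fluctuation.

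The change does not set a repeat interval or make PT mandatory for either enzyme. If the sponsor wants those, they need separate wording.
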